Rationale: Patients with haematological malignancies and chemotherapy induced prolonged neutropenia are at risk for severe bacterial and fungal infections. These opportunistic infections can result in prolonged hospital stay, increases costs and greater mortality. Voriconazole has now been recommended as the first line agent for invasive pulmonary aspergillosis (IA). Retrospective observational studies of voriconazole serum concentration suggest that serum concentration correlate with toxicity and clinical response. These observations were however made in small series of patients and data were collected retrospectively. These inherent methodological flaws make it impossible to draw definite conclusions about the effect of voriconazole serum concentration monitoring on the outcome of IA, and therefore considered insufficient proof to recommend voriconazole concentration determination in blood as standard of care. The impact that so-called serum concentration guided dosing of voriconazole will have on treatment success can only be evaluated through a prospective randomized clinical trial.

Objective: The objective of this study proposal is to determine whether pharmacologic optimization of voriconazole by means of therapeutic drug monitoring (TDM) results in improved patient outcomes (efficacy and safety) and is more cost-effective compared to the current standard of care.

Study design: we designed a prospective stratified cluster randomized cross-over trial of therapeutic drug monitoring in patients with haematological disease who have developed IA. The order of periods (TDM or standard of care, each 12 months) will be randomized per centre.

Study population: Patients with haematological malignancies and possible, probable or proven IA according to EORTC criteria.

Intervention (if applicable): In the intervention group the voriconazole dosage will be adjusted to achieve trough blood concentrations in a predefined window of 2-5 mg/L. In the control group voriconazole will be dosed according to product leaflet.

Main study parameters/endpoints: The primary clinical endpoint will be a global response consisting of a combined endpoint of toxicity and response to therapy (clinical, microbiologic and radiologic responses) 28 days after starting treatment with voriconazole. A sample size of n=192 is needed to detect a 20% absolute reduction in the number of

treatment failures (40% to 20 %) compared to control. It total 200 patients will be included to compensate a loss during follow up. A cost-effectiveness analysis will be performed from a hospital and societal perspective. The cost effectiveness ratio will depict the extra amount of money, which has to be invested to prevent the therapeutic failure for a single patient, with TDM guided voriconazole treatment compared to standard of care.

Nature and extent of the burden and risks associated with participation, benefit and group relatedness: There is no additional risk compared to standard of care. The study is designed to optimize standard of care by dosing on serum concentration and therefore possibly preventing side effects and increasing efficacy. The extra sample needed for TDM are no extra burden as these patients are often monitored for clinical or pharmacological parameters. The sample is taken during regular sampling for routine laboratory parameters like electrolyte, hepatic function etc. The advantage of choosing this sampling moment (early morning) is that no extra vena puncture has to be performed.

1. INTRODUCTION AND RATIONALE

Patients with prolonged and severe neutropenia (neutrophils $<0.5 \times 10^9/L$ for >10 days), are at risk for life-threatening infections especially invasive pulmonary aspergillosis. The risk of invasive Aspergillosis (IA) increases with the severity and duration of neutropenia. Patients treated for haematologic malignancies with intensive chemotherapy and hematopoietic stem cell transplant recipients are at particularly high risk [6-10]. Other risk factors for IA include Graft-Versus-Host Disease and its treatment with corticosteroids, previous invasive mould infection and high environmental exposure to fungal spores in ambient air [11-14]. As the reported response to antifungal therapy is low (50%) and mortality high (30-50%) there is still an urgent need to improve treatment [23-25].

Every year, about 200 patients in the Netherlands with haematological malignancies, are treated with voriconazole for invasive fungal infection. This translates into 15-25 patients per centre annually. When patients encounter an invasive fungal infection the chemotherapy for the haematological malignancy is often interrupted or sometimes continued in a reduced intensity. This results in a suboptimal treatment of the underlying malignancy. The results of antifungal therapy are far from optimal with response rates for voriconazole and lipid amphotericin B being approximately 50%. The overall mortality at 12 weeks is still 30-50%. Clearly, there is a dire need to improve treatment outcome for IA. Haematologists, in consultation with an infectious diseases specialists, medical microbiologists and hospital pharmacists put effort in optimizing treatment in this critically ill patient population.

Voriconazole is the first line treatment of IA among patients with haematological malignancies and hematopoietic stem cell transplant recipients according to recent international guidelines [43] as reported in a large randomised trial [16]. Recent observational studies suggest that voriconazole serum concentrations of at least 1 to 2.0 mg/L are associated with improved clinical outcome [18, 19, 42]. This clinical finding is supported by the in-vitro susceptibility of *Aspergillus fumigatus* to voriconazole [20]. On the other hand high trough concentrations exceeding 5 mg/L are associated with toxicity, mainly neurological and hepatotoxicity [40, 42,46]. It has also been shown that the inter-individual variation of voriconazole plasma levels is significant due to hereditary factors that influence the rate of clearance of the drug. Consequently, the guidelines for the treatment of IA published recently by the Infectious Diseases Society of America (IDSA) recommend monitoring of voriconazole concentration levels and adjusting dosage accordingly as an option for patients not responding to the standard weight-based dosing of voriconazole. This may be caused by sub-therapeutic serum concentrations or treatment discontinuation due to side effects that might be caused by toxic serum concentrations. Monitoring of serum

concentrations and adjusting the dose will be an alternative to switching to other antifungal agents such as a lipid formulation of amphotericin B, caspofungin or posaconazole [43].

Furthermore, voriconazole treatment is relatively expensive itself (€400/day for parenteral treatment) and suboptimal use can be expected to result in therapeutic failure, and additional costs incurred by the need for more expensive salvage antifungal therapy and prolonged hospital stay. We hypothesize that dosing of voriconazole based on serum concentration (so-called therapeutic drug monitoring) will result in improved clinical outcome of patients with IA, by reducing the risk of therapeutic failure and toxicity and that this will be cost-effective [39, 41, 43]. A multi-center randomized controlled clinical trial was designed to test this hypothesis [21, 22, 41].

As too low (< 2 mg/L) or too high (> 5 mg/L) voriconazole serum concentrations are observed in 25-60% and 10-25% of patients respectively TDM has the potential to improve treatment outcome. Optimizing antifungal therapy through concentration based dosing of voriconazole fits within the theme of pharmacotherapy as it is likely to optimize efficacy of treatment in the individual patient. This approach could be cost-effective through the prevention of toxicity and treatment failure that requires the use of more expensive antifungal agents for salvage therapy. At present, no randomized trials have addressed the question whether the use of TDM improves the outcome of voriconazole therapy. We hypothesize that therapeutic failure, now estimated around 40% can be reduced by half - i.e., to 20% using TDM. Failure is defined clinically. In a previous randomised trial with voriconazole in a dosage according to product leaflet the response to therapy was: complete in 20%, partial in 30%, stable infection in 10% and progressive infection (failure) in 40% [16]. As TDM is most likely to benefit patients with low voriconazole trough levels who are not responding or in patients with high trough levels who stopped because of side effects a reduction of failure from 40% to 20% can be anticipated to occur with TDM.

At present, there is a paucity of well-conducted studies on the added value and cost-effectiveness of TDM in general [26,27], and no data exists on the costs-effectiveness of TDM in patients with IA in particular. The costs of TDM in the present study proposal are estimated to be between €315 and €790 per patient per treatment episode, depending on the time elapsed until an adequate voriconazole serum level is reached. The costs of voriconazole may be higher in the early phase of therapy compared to the standard dosing scheme, due to an increase in dosage. However, in the latter phase of therapy these costs could be reduced by a switch from intravenous to oral therapy, or a shorter duration of treatment as a consequence of a better response to treatment. Furthermore, an increase in

treatment response will obviate the use of more expensive alternative antifungal drugs as salvage therapy. The costs of oral voriconazole are about €70 a day (200mg bid), compared to €540 a day for intravenous therapy (4 mg/kg bid). In a retrospective study management costs of 80 IA cases among 269 patients with AML-MDS patients undergoing intensive chemotherapy were assessed. IA was categorized according to revised EORTC-MSG definitions. Costs were documented from a hospital and societal perspective. Treatment with voriconazole was given orally from day 1 onwards whenever oral intake was possible. Total IA-related management costs were €10765 and €26182 respectively for possible and probable/proven IA. Based on these findings and the available literature [16,17], we hypothesize that treatment based on TDM will reduce the mean length of hospital stay by 3 days per patient, saving about € 1500 per patient per treatment course. Earlier transfer from the intensive care unit to the hospital ward will save an additional €1250 per patient per day. In addition, we expect fewer drug related adverse events and therapeutic failure in the TDM episode, which will lead to less additional diagnostic testing and additional therapy. Preventing the switch to more expensive antifungal therapy can save €200-500 per day of treatment. This will have a positive effect on the balance between costs and benefits.

2. OBJECTIVES

Primary objective

The aim of this study is to demonstrate a 20% absolute reduction in the number of treatment failures (40% to 20%) with the use of voriconazole therapeutic drug monitoring in patients with haematological malignancies suffering from invasive Aspergillosis.

Secondary objective

In addition we want to study the balance between costs from hospital and societal perspective and effects.

3. STUDY DESIGN

As the number of patients treated for invasive aspergillosis in each hospital is limited, a multi centre set up is required to have a study powered to detect a clinically relevant difference in outcome between the intervention group and the control group. For this study a cluster randomized design - instead of a randomisation at patient level - was chosen to minimize logistic problems, optimize inclusion of patients and limit bias during the study. Blinding the intervention would increase the costs of the study considerably without providing better results. The cross-over design was chosen to diminish influences by centre, as the inter-centre variability in facility and treatment can influence outcome of treatment. Differences which are found can now be attributed solely to the intervention as the centre serves as its own control. As this study will be performed in several centres with random start with standard care or with TDM-tailored treatment, we anticipate that the time-based biases will be negligible. To diminish the carry-over effect from one period to the next a wash-out period of 28 days is established, which equals the time of start of treatment until evaluation on the primary endpoint. This prevents that two treatment protocols, intervention and control are operational at the same time. For these reasons we choose a cluster randomized cross-over design in which every cluster receives both interventions during two consecutive periods (TDM and standard care, 12 months each). This longitudinal design was previously successfully used in the Netherlands [32]. Randomization by a computer-generated randomization system determines the sequence within in each cluster. In this way the variability between clusters is taken into account, this results in an improved power. The randomization will be stratified to obtain equally balanced clusters with respect to experience and size. At six months, inclusion will be evaluated and it will be estimated whether duration per period has to be increased or decreased and whether the clusters are still balanced. The intervention (TDM) consists of taking serum samples at day three of treatment, measuring the voriconazole serum levels and adjusting the dosage to reach the therapeutic window. Dosing of voriconazole will be done during the control period according to the product brochure.

Response to treatment will be evaluated at day 7 (fever), day 28 (primary endpoint) and at 12 weeks after start of therapy (mortality). Assessment of quality of life will be performed after release from the hospital at different time points (2 weeks, 3 months, 6 months and 1 year). Cost effectiveness from hospital perspective will be evaluated after release from the hospital. Cost effectiveness from societal perspective will be evaluated after 1 year after start of the treatment.

An expert panel (EPHO) of three specialists in the field of haemato-oncology, radiology, and mycology, and who are unaware of allocation to either of the two arms of the study (intervention or control), will classify all documented aspergillosis according to the EORTC/MSG criteria [33,45] and will report the likelihood whether fever was caused by: drug fever (e.g. cytarabine), mucositis, malignancy, Graft –Versus-Host Disease, or infection and a likelihood whether mortality was caused by fungal infection or progression of malignancy or any other cause, using protocol-defined criteria. Likelihood will be presented on a scale of 0/3 till 3/3. The evaluation of endpoints by an independent expert panel excludes investigators' bias [34, 35]. At the end of the study the EPHO, unaware of allocation to either of the two arms of the study (intervention or control), will review each patient on the primary and the following secondary endpoints 1, 2, 5 and 6. After the review of the independent expert panel the multi disciplinary study team, consisting of haematologists, infectious diseases specialists, radiologists, pharmacists, medical microbiologists, a biostatistician and a MTA expert will analyze the data on all endpoints using the outcome of the pre-screening of the expert panel.

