7.1.2 Secondary study parameters/endpoints (if applicable)

- 1) mortality at day 28 and week 12 of therapy due to fungal infection, overall mortality at 28 days and 12 weeks.
- 2) resolution of neutropenic fever, defined as percentage of patients with a oral temperature of $<38\text{ }^{\circ}\text{C}$ at day 7 of voriconazole treatment [17]; time (in days) to resolve fever is also noted.
- 3) percentage of voriconazole serum concentrations within the targeted window of 2-5mg/L during therapy based on repeated measurements in time.
- 4) percentage switched to salvage therapy (i.e. amphotericin B or one of its lipid or liposomal formulations; or echinocandin (e.g., caspofungin/anidulafungin) or other triazole (e.g., posaconazole); or measured concentration level in control arm during treatment for toxicity or failure)

- 5) side effects (visual disturbance and liver enzymes) Side effects leading to drug discontinuation.
- 6) time (in days) of to global response as defined under the primary endpoint definition after the start of voriconazole
- 7) The evaluation of cost-effectiveness (hospital and societal per perspective) of voriconazole TDM in patients with invasive aspergillosis will be an integral part of this project.

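### The salvage-switch endpoint (secondary endpoint 4) lies outside the blinded panel's review, states no reason criterion for a drug change, and has one component that only control patients can meet

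*Protocol*

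**What the plan says.** Section 3 declines to blind treatment: "Blinding the intervention would increase the costs of the study considerably without providing better results". It relies instead on a panel of three specialists, unaware of allocation, who at the end of the study "will review each patient on the primary and the following secondary endpoints 1, 2, 5 and 6". The study team then analyses all endpoints using the panel's output.

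Section 7.1.2 lists seven secondary endpoints. Endpoint 4 is the "percentage switched to salvage therapy (i.e. amphotericin B or one of its lipid or liposomal formulations", followed by an echinocandin, "or other triazole (e.g., posaconazole"), and finally "or measured concentration level in control arm during treatment for toxicity or failure". The two other endpoints not on the panel's list are endpoint 3, "percentage of voriconazole serum concentrations within the targeted window of 2-5mg/L during therapy based on repeated measurements in time", and endpoint 7, "The evaluation of cost-effectiveness (hospital and societal per perspective) of voriconazole TDM in patients with invasive aspergillosis".

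Two other places bear on the definition. Section 1 speaks of salvage therapy as what toxicity and treatment failure make necessary. Section 6.5 lets the attending physician ask for a concentration under stated toxicity and failure conditions.

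**The concern.** A switch of antifungal is a decision by a treating physician who knows whether the centre is in its TDM or its standard-care period. For the other clinical endpoints, a blinded panel stands between that knowledge and the recorded result. For endpoint 4 nothing does.

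The definition adds two difficulties:

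- The drug components are fixed by which drug was given. As worded, they do not separate a change for failure or toxicity from a change made for some other reason, such as a drug interaction.
- The last component is restricted to control patients. A control patient who stays on voriconazole but has a level measured for toxicity or failure is an event. No TDM patient can become an event by that route.

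At stake is whether a difference in endpoint 4 can be read as fewer patients needing salvage under TDM.

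**Working it through.** **1. Which endpoints the panel sees (section 3 against section 7.1.2)**

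- On the list: the primary endpoint, and secondary endpoints 1 (mortality), 2 (fever), 5 (side effects, including those leading to discontinuation) and 6 (time to response).
- Off the list: 3 (concentrations within the window, a laboratory measure), 4 (switch to salvage) and 7 (cost-effectiveness).
- With 3 and 7 set aside as laboratory and economic, endpoint 4 is the one clinical endpoint not reviewed.

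**2. What makes a patient an event under endpoint 4**

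- Change to a listed drug: possible in both arms; no reason stated.
- Concentration measurement: possible in the control arm only; reason stated (toxicity or failure).

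The reason thus qualifies only the component that cannot occur in the TDM arm.

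**3. Denominator, checked against the plan's own figure**

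Section 4.4 gives 12 centres × 16 patients = 192, hence 192/2 = 96 per arm if the periods are equal in size. For 40% against 20%, two-sided 5% and 80% power, the usual formula gives 82 per arm, 164 in total. With 16/2 = 8 patients per cluster-period, cluster-periods treated as independent, and the upper correlation of 0.02, the design effect is 1 + (8 − 1) × 0.02 = 1.14. Then 164 × 1.14 = 187, close to the stated 192, and power with 96 per arm is 81.4% against the stated figure of about 80%. The sample size is not in question; it only supplies the denominator and design effect used below.

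**4. Illustration of size (assumed rates; the protocol gives none for endpoint 4)**

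*(a) Reclassified drug changes.* Five in one arm: 5/96 = 5.2 percentage points in that arm. This can go in either direction.

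*(b) Events added to the control arm only.* Let the true salvage rate be s in both arms, and let a further fraction d of the remaining control patients be counted, for example through the concentration measurement. The control rate becomes s + (1 − s)d. With s = 20%:

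- d = 5%: 0.20 + 0.80 × 0.05 = 24%, a difference of 4 points.
- d = 10%: 0.20 + 0.80 × 0.10 = 28%, a difference of 8 points.
- d = 20%: 0.20 + 0.80 × 0.20 = 36%, a difference of 16 points.

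The effective size is n = 96/1.14 = 84.2 per arm. The chance of a significant result favouring TDM is Φ[(Δ − 1.96·SE0)/SE1], where SE0 = √[2p̄(1 − p̄)/n] uses the mean rate p̄, and SE1 = √{[p_c(1 − p_c) + s(1 − s)]/n} uses the two separate rates.

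For d = 10%: p̄ = 0.24, SE0 = 0.0658, SE1 = 0.0655, and (0.08 − 1.96 × 0.0658)/0.0655 = −0.75, which gives about 23%. For d = 5% and 20% the same formula gives about 9% and 64%. With s from 10% to 30% and d from 5% to 20%, the range is 7% to 85%. With no true difference and no such added events, the figure should be 2.5%.

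**The case against.** Several objections carry weight.

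- **The word salvage already implies a reason.** The listed drugs say which agents qualify; they do not cancel the word, and section 1 connects it with toxicity and failure. This stands as a limit. A reader might infer that the protocol means every change of drug to count, including one for an interaction or after a good response. It does not say so. The only step-down it describes is from intravenous to oral voriconazole, which is not a listed switch. What the text supports is that no reason criterion is stated for the drug components.
- **Avoiding a switch is what TDM is for.** Section 1 says that "adjusting the dose will be an alternative to switching to other antifungal agents". A switch avoided because the level was corrected is a treatment effect, so that sentence is not evidence of bias. Nor can panel review recover a switch that never happened.
- **The claim about investigators' bias is not contradicted.** A reader might set the omission of endpoint 4 against the statement in section 3 that panel evaluation excludes such bias. That statement concerns endpoints the panel evaluates and makes no claim about the others.
- **The cost argument is unaffected.** A reader might infer that mislabelled switches distort the cost comparison. Section 7.1.3 costs the medication used, so the label given to a switch changes no cost.
- **The facts are recorded, and reasons may be coded elsewhere.** Whether a listed drug was given needs no adjudication, and the case report form or the analysis plan may collect reasons. The panel also already judges failure and discontinuation for side effects. This lowers the weight of the point. It does not remove it, because the protocol itself fixes both the panel's list and the endpoint's wording.
- **The control-arm measurement has a rationale.** It marks control patients whose management departed from unmonitored dosing. It is worth recording, but as part of a between-arm percentage it is zero in one arm by definition.
- **Simply adding endpoint 4 to the list would harm blinding.** A concentration request of that kind identifies a control patient to the panel that also judges the primary endpoint. This stands and shapes the fix.

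**Conclusion.** The point holds in a limited form. Endpoint 4 is the only clinical secondary endpoint outside blinded review, its drug components carry no stated reason criterion, and its last component can add events only to the control arm. In an open-label trial, changes made for reasons other than failure or toxicity can therefore be counted as salvage, and the between-arm percentage does not compare like with like.

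The size is unknown. The 5.2 points and the 4 to 16 points above rest on assumed counts and rates, on equal arms of 96 and, for the probabilities, on a design effect of 1.14. They show what would follow if such events occurred, not that they will. The one-sided component is the more serious of the two definitional problems, because its direction is built in.

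A reader might go further and conclude that unblinded physicians' choices decide this endpoint and that panel review would remove the bias. The documents support neither. Review can reduce misclassification of switches that were made; it cannot undo a switch or restore one that was avoided. The primary endpoint, the sample size and the cost analysis are not affected by this defect. It is a minor, worthwhile correction to one secondary endpoint.

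**What to change.** - In section 3, add to the panel's remit a blind classification of each change to a listed antifungal as failure, toxicity or other reason. Use patient files from which drug levels and concentration requests have been removed.
- In section 7.1.2, state that endpoint 4 counts changes classified as failure or toxicity, and report all changes to a listed drug beside it, by arm.
- Take the control-arm concentration measurement out of the between-arm comparison. Report it separately, as a description of the control arm, and do not show it to the panel.
- State in the report that the classification does not address switches avoided through knowledge of the arm.

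The cost is an amended sentence in each of the two sections, one field on the panel form, slightly more panel time and the work of redacting the files. The panel already reviews every patient, and reporting all changes alongside means that no information is lost.
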